2.4 IMMUNOGENICITY OBJECTIVES

The immunogenicity objective for this study is to evaluate the immune response to lampalizumab through the analysis of the incidence of anti-therapeutic antibodies (ATAs) during the study relative to the prevalence of ATAs at baseline.

The exploratory immunogenicity objective for this study is to evaluate potential effects of ATAs on the efficacy, safety, biomarker, or PK endpoints.

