6.6 IMMUNOGENICITY ANALYSES

The immunogenicity analyses will include patients with at least one predose (*defined as prior to the first dose in the extension study for the prior sham patients, and prior to the first dose in the parent study for the prior lampalizumab patients*) and one postdose ATA assessment. *The analysis will be summarized by treatment group in the parent study.*

The number and proportion of ATA-positive and ATA-negative patients during this study will be summarized by treatment group. The relationship between ATA status and the safety, efficacy, PK, and biomarker endpoints will be analyzed and reported descriptively in subgroup analyses. Patients are considered to be ATA--positive if they are ATA-negative at baseline (*defined as the last measurement prior to the first dose in the extension study for the prior sham patients, and the last measurement prior to the first dose in the Parent study for the prior lampalizumab patients*) but develop an ATA response following study drug administration (i.e., treatment-induced ATA response) or if they are ATA-positive at baseline and the titer of one or more post-baseline samples is at least 4-fold greater (i.e., ≥ 0.60 titer units) than the titer of the baseline sample (i.e.,

treatment-enhanced ATA response). Patients are considered to be ATA-negative if they are ATA-negative at baseline and all post-baseline samples are negative or if they are ATA-positive at baseline but do not have any post-baseline samples with a titer that is at least 4-fold greater than the titer of the baseline sample (i.e., treatment unaffected).

The relationship between ATA status and the safety, efficacy, PK, and biomarker endpoints will be analyzed and reported descriptively via subgroup analyses.

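### For relating antibody status to outcomes, Section 6.6 pools patients with pre-existing, unenhanced antibody with never-positive patients; showing them separately is a cheap improvement

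*Combined protocol and SAP*

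**What the plan says.** Section 6.6 defines two routes to the negative label. The first is the expected one: "Patients are considered to be ATA-negative if they are ATA-negative at baseline and all post-baseline samples are negative". The second covers patients for whom "they are ATA-positive at baseline but do not have any post-baseline samples with a titer that is at least 4-fold greater" than at baseline, a class the section names treatment unaffected. The positive label covers treatment-induced responses (baseline negative, then a response after study drug) and treatment-enhanced responses (baseline positive, with a later titer "at least 4-fold greater (i.e., ≥ 0.60 titer units) than the titer of the baseline sample").

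Baseline depends on prior treatment. It is "the last measurement prior to the first dose in the Parent study for the prior lampalizumab patients" and "the last measurement prior to the first dose in the extension study for the prior sham patients". In both cases it precedes the patient's first lampalizumab injection.

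Section 6.6 then states, twice in similar words, how the label is used: "The relationship between ATA status and the safety, efficacy, PK, and biomarker endpoints will be analyzed and reported descriptively via subgroup analyses". It names no other ATA status, no baseline-positive subgroup and no analysis by titer.

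Section 2.4 sets two immunogenicity objectives. One compares ATA incidence during the study with ATA prevalence at baseline. The other, exploratory, is to "evaluate potential effects of ATAs on the efficacy, safety, biomarker, or PK endpoints".

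**The concern.** The two objectives need different groupings. Incidence asks who developed or boosted an antibody response on treatment, and the two-level rule answers that. The exploratory objective asks whether antibody is associated with outcomes. There, the natural reference is patients in whom no antibody was found. Under Section 6.6 the reference also contains patients in whom antibody was measured before any lampalizumab and whose titer did not rise 4-fold.

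Two things follow. If pre-existing antibody acts in the same direction as induced or enhanced antibody, the contrast between positive and negative patients is diluted. And no planned table shows the outcomes of patients with pre-existing, unenhanced antibody. The second matters more here. Prior sham patients receive lampalizumab for the first time in this study, Section 5.1 lists ocular inflammation as a potential safety issue, and those among them with pre-existing antibody are an obvious group to look at.

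**Working it through.** **The plan's own figure.** A 4-fold rise is given as 0.60 titer units. On a log10 scale, log10(4) = 0.602, and 10^0.60 = 3.98. The figure reproduces, so titer units are log10 and the threshold is consistent.

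**Which antibody carriers fall where**, reading Section 6.6 against its baseline definitions:

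| Patient | Label in 6.6 |
|---|---|
| Negative at baseline and at all later samples | negative |
| Positive before first lampalizumab, no 4-fold rise | negative |
| Positive before first lampalizumab, 4-fold rise | positive |
| Negative before first lampalizumab, positive later, including in the parent study | positive |

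Only the second row is at issue.

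**Formula.** Let w be the share of the ATA-negative group that is treatment unaffected. If those patients carry the same risk as the positive group, then

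- rate shown for negatives = (1 − w) × risk without antibody + w × risk with antibody
- risk difference shown = true risk difference × (1 − w)

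**Inputs.** The documents give no baseline ATA prevalence, no emergent incidence and no event risk by ATA status. All of the following are assumptions, except that 1800 is the enrolment cap in Section 3.1.2: pre-existing unenhanced ATA in 2–10% of patients (36–180), treatment-emergent ATA in 2–5% (36–90), and an ocular inflammation risk of 2% without antibody and 6% with any antibody. The true ratio is 3.0 and the true difference 4.0 points.

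| Pre-existing / emergent | w | Rate shown for negatives | Ratio | Difference (points) |
|---|---|---|---|---|
| 2% / 2% | 36/1764 = 2.0% | (1728×2% + 36×6%)/1764 = 2.08% | 2.88 | 3.92 |
| 5% / 5% | 90/1710 = 5.3% | (1620×2% + 90×6%)/1710 = 2.21% | 2.71 | 3.79 |
| 10% / 5% | 180/1710 = 10.5% | (1530×2% + 180×6%)/1710 = 2.42% | 2.48 | 3.58 |

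**Wider range.** Now assume baseline prevalence b from 1% to 20%, 10% of baseline positives enhanced, and 5–10% (i) of baseline negatives induced. Then w = 0.9b / [0.9b + (1 − b)(1 − i)] runs from 0.9% to 20.0%. With an assumed risk of 10% in carriers and 5% in others, the true difference of 5.0 points is shown as 4.95 to 4.00, and the true ratio of 2.00 as 1.98 to 1.67. In both sets the proportional loss in the risk difference is w, which is close to the baseline prevalence.

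**Against sampling error.** With 36–90 positive patients at 6%, about 2 to 5 events are expected. Exact 95% intervals are 0.7–18.7% for 2/36 and 1.8–12.5% for 5/90. The shift of 0.1–0.4 points in the comparator rate is small beside that.

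**The case against.** The strongest reply is that nothing of consequence depends on this. The objective is exploratory, the analyses are descriptive, every patient receives lampalizumab, and Section 6.3 already urges caution in reading the safety results. The dilution is small on any plausible inputs and lost in sampling error. Baseline positivity is not ignored either: Section 2.4 sets incidence against baseline prevalence, and Section 6.6 names the treatment-unaffected class. Individual inflammation events are recorded whatever the label. All of this stands, and it limits the weight of the point. It does not supply the missing display of outcomes by that class. Section 6.4 defers detail to a Data Analysis Plan, but Section 6.6 contains no such deferral.

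A reader might infer three stronger things that the documents do not support.

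- *That antibodies raised by lampalizumab in the parent study are hidden in the negative group.* They are not. Baseline for prior lampalizumab patients precedes the parent study, so a patient negative then and positive later is classed ATA-positive.
- *That treatment-unaffected patients had antibody present at every injection.* This cannot be known. Appendix 1 takes the Day 1 sample from the parent study and then schedules ATA sampling only at Week 48, Week 96 and early termination. The class also includes patients whose titer fell or disappeared. For prior lampalizumab patients the baseline sample is about two years older than extension Day 1.
- *That any antibody effect is necessarily diluted.* That holds only if pre-existing antibody acts in the same direction as induced or enhanced antibody. If it has no clinical effect, pooling dilutes nothing.

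**Conclusion.** The point holds as a limited one. The two-level status is right for treatment-emergent incidence and less suitable for the exploratory question of what antibodies do. It mixes some carriers of pre-existing antibody into the comparator and gives their outcomes no separate display.

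The loss in the risk difference is about the baseline ATA prevalence: 2% to 10.5% of the difference for assumed pre-existing unenhanced ATA of 2–10%, with the risk ratio falling from 3.0 to between 2.9 and 2.5. This rests on assumed prevalences and risks, on enrolment at the cap, and on pre-existing antibody acting like induced antibody. It would be wrong to conclude that the primary safety objective is compromised: no test, error rate or primary conclusion is touched. I would class this as a cheap improvement.

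**What to change.** Keep the two-level rule for the incidence table. In Section 6.6, add a sentence stating that the analyses relating ATA to safety, efficacy, PK and biomarkers will use three groups:

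- (a) ATA-negative at baseline and at all later samples, as the reference;
- (b) ATA-positive at baseline and treatment unaffected, with the number still positive at any extension sample shown;
- (c) treatment-induced or treatment-enhanced.

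The groups do not overlap and cover every case that Section 6.6 defines. No new sample, assay or derivation is needed. The count of patients still positive in (b) is there because the group mixes persistent carriers with patients who turned negative, and the reader needs to see how many of each there are.

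The cost is one sentence and one extra column. Group (b) may be small: under the assumptions above, 36–180 patients and about 2 to 11 events (36 × 6% = 2.2; 180 × 6% = 10.8). It may therefore have to be reported as counts only.

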6.7 HANDLING OF MISSING DATA

All efforts will be made to minimize missing data; no imputation will be performed for the missing data for the analyses.

6.8 OPTIONAL INTERIM ANALYSIS

Interim safety analyses will be conducted periodically by independent Data Monitoring Committee (iDMC) to monitor safety and study conduct of this extension study. No formal interim efficacy/futility analyses are planned. Exploratory efficacy and/or safety analyses may be performed with interim data (e.g., to support regulatory submissions).

7. DATA COLLECTION AND MANAGEMENT

7.1 DATA QUALITY ASSURANCE

The Sponsor will be responsible for data management of this study, including quality checking of the data. Data entered manually will be collected via the EDC using eCRFs. Sites will be responsible for data entry into the EDC system. In the event of discrepant data, the Sponsor will request data clarification from the sites, which the sites will resolve electronically in the EDC system.

The Sponsor will produce an EDC Study Specification document that describes the quality checking to be performed on the data. Central laboratory data and Reading Center Images data will be sent directly to the Sponsor using the Sponsor's standard procedures to handle and process the electronic transfer of these data.

eCRFs and correction documentation will be maintained in the EDC system's audit trail. System backups for data stored by the Sponsor, and records retention for the study data will be consistent with the Sponsor's standard procedures.

The Sponsor will supply eCRF specifications for this study.

Data from PRO questionnaires will be recorded on worksheets, and the data will be entered into the EDC by sites.

7.2 ELECTRONIC CASE REPORT FORMS

eCRFs are to be completed through use of a Sponsor-designated EDC system. Sites will receive training and have access to a manual for appropriate eCRF completion.

eCRFs will be submitted electronically to the Sponsor and should be handled in accordance with instructions from the Sponsor.

All eCRFs should be completed by designated, trained site staff. eCRFs should be reviewed and electronically signed and dated by the investigator or a designee.

At the end of the study, the investigator will receive patient data for his or her site in a readable format on a compact disc that must be kept with the study records. Acknowledgement of receipt of the compact disc is required.

7.3 SOURCE DATA DOCUMENTATION

Study monitors will perform ongoing source data verification to confirm that critical protocol data (i.e., source data) entered into the eCRFs by authorized site personnel are accurate, complete, and verifiable from source documents.

Source documents (paper or electronic) are those in which patient data are recorded and documented for the first time. They include, but are not limited to, hospital records; clinical and office charts; laboratory notes; memoranda; PROs; evaluation checklists; pharmacy dispensing records; recorded data from automated instruments; copies of transcriptions that are certified after verification as being accurate and complete; microfiche; photographic negatives; microfilm or magnetic media; X-rays; patient files; and records kept at pharmacies, laboratories, and medico-technical departments involved in a clinical trial.

Before study initiation, the types of source documents that are to be generated will be clearly defined in the Trial Monitoring Plan. This includes any protocol data to be entered directly into the eCRFs (i.e., no prior written or electronic record of the data) and considered source data.

Source documents that are required to verify the validity and completeness of data entered into the eCRFs must not be obliterated or destroyed and must be retained per the policy for retention of records described in Section 7.5.

To facilitate source data verification, the investigators and institutions must provide the Sponsor direct access to applicable source documents and reports for trial-related monitoring, Sponsor audits, and IRB/EC review. The study site must also allow inspection by applicable health authorities.

7.4 USE OF COMPUTERIZED SYSTEMS

When clinical observations are entered directly into a study site's computerized medical record system (i.e., in lieu of original hardcopy records), the electronic record can serve as the source document if the system has been validated in accordance with health authority requirements pertaining to computerized systems used in clinical research. An acceptable computerized data collection system allows preservation of the original entry

of data. If original data are modified, the system should maintain a viewable audit trail that shows the original data as well as the reason for the change, name of the person making the change, and date of the change.

7.5 RETENTION OF RECORDS

Records and documents pertaining to the conduct of this study and the distribution of IMP, including eCRFs, PRO data, ICFs, laboratory test results, and medication inventory records, must be retained by the Principal Investigator for at least 15 years after completion or discontinuation of the study or for the length of time required by relevant national or local health authorities, whichever is longer. After that period of time, the documents may be destroyed, subject to local regulations.

No records may be disposed of without the written approval of the Sponsor. Written notification should be provided to the Sponsor prior to transferring any records to another party or moving them to another location.

8. ETHICAL CONSIDERATIONS

8.1 COMPLIANCE WITH LAWS AND REGULATIONS

This study will be conducted in full conformance with the ICH E6 guideline for GCP and the principles of the Declaration of Helsinki or the laws and regulations of the country in which the research is conducted, whichever affords the greater protection to the individual. The study will comply with the requirements of the ICH E2A guideline (Clinical Safety Data Management: Definitions and Standards for Expedited Reporting). Studies conducted in the United States or under a U.S. Investigational New Drug (IND) Application will comply with U.S. FDA regulations and applicable local, state, and federal laws. Studies conducted in the European Union or European Economic Area will comply with the E.U. Clinical Trial Directive (2001/20/EC).

8.2 INFORMED CONSENT

The Sponsor's sample ICF (and ancillary sample ICFs, if applicable) will be provided to each site. If applicable, it will be provided in a certified translation of the local language. The Sponsor or its designee must review and approve any proposed deviations from the Sponsor's sample ICFs or any alternate consent forms proposed by the site (collectively, the "Consent Forms") before IRB/EC submission. The final IRB/EC-approved Consent Forms must be provided to the Sponsor for health authority submission purposes according to local requirements.

If applicable, the ICF will contain separate sections for any optional procedures. The investigator or authorized designee will explain to each patient the objectives, methods, and potential risks associated with each optional procedure. Patients will be told that they are free to refuse to participate and may withdraw their consent at any time for any reason. A separate, specific signature will be required to document a patient's

agreement to participate in optional procedures. Patients who decline to participate will not provide a separate signature.

The Consent Forms must be signed and dated by the patient before his or her participation in the study. The case history or clinical records for each patient shall document the informed consent process and that written informed consent was obtained prior to participation in the study.

The Consent Forms should be revised whenever there are changes to study procedures or when new information becomes available that may affect the willingness of the patient to participate. The final revised IRB/EC-approved Consent Forms must be provided to the Sponsor for health authority submission purposes.

Patients must be re-consented to the most current version of the Consent Forms (or to a significant new information/findings addendum in accordance with applicable laws and IRB/EC policy) during their participation in the study. For any updated or revised Consent Forms, the case history or clinical records for each patient shall document the informed consent process and that written informed consent was obtained using the updated/revised Consent Forms for continued participation in the study.

A copy of each signed ICF must be provided to the patient. All signed and dated Consent Forms must remain in each patient's study file or in the site file and must be available for verification by study monitors at any time.

For sites in the United States, each ICF may also include patient authorization to allow use and disclosure of personal health information in compliance with the U.S. HIPAA of 1996. If the site utilizes a separate Authorization Form for patient authorization for use and disclosure of personal health information under the HIPAA regulations, the review, approval, and other processes outlined above apply except that IRB review and approval may not be required per study site policies.

8.3 INSTITUTIONAL REVIEW BOARD OR ETHICS COMMITTEE

This protocol, the Consent Forms, any information to be given to the patient, and relevant supporting information must be submitted to the IRB/EC by the Principal Investigator and reviewed and approved by the IRB/EC before the study is initiated. In addition, any patient recruitment materials must be approved by the IRB/EC.

The Principal Investigator is responsible for providing written summaries of the status of the study to the IRB/EC annually or more frequently in accordance with the requirements, policies, and procedures established by the IRB/EC. Investigators are also responsible for promptly informing the IRB/EC of any protocol amendments (see Section 9.6).

In addition to the requirements for reporting all adverse events to the Sponsor, investigators must comply with requirements for reporting serious adverse events to the

local health authority and IRB/EC. Investigators may receive written IND safety reports or other safety-related communications from the Sponsor. Investigators are responsible for ensuring that such reports are reviewed and processed in accordance with health authority requirements and the policies and procedures established by their IRB/EC, and archived in the site's study file.

8.4 CONFIDENTIALITY

The Sponsor maintains confidentiality standards by coding each patient enrolled in the study through assignment of a unique patient identification number. This means that patient names are not included in datasets that are transmitted to any Sponsor location.

Patient medical information obtained by this study is confidential and may be disclosed to third parties only as permitted by the ICF (or separate authorization for use and disclosure of personal health information) signed by the patient, unless permitted or required by law.

Medical information may be given to a patient's personal physician or other appropriate medical personnel responsible for the patient's welfare, for treatment purposes.

Data generated by this study must be available for inspection upon request by representatives of national and local health authorities; Sponsor monitors, representatives, and collaborators; and the IRB/EC for each study site, as appropriate.

8.5 FINANCIAL DISCLOSURE

Investigators will provide the Sponsor with sufficient, accurate financial information in accordance with local regulations to allow the Sponsor to submit complete and accurate financial certification or disclosure statements to the appropriate health authorities. Investigators are responsible for providing information on financial interests during the study and for 1 year after completion of the study (i.e., LPLV).

9. STUDY DOCUMENTATION, MONITORING, AND ADMINISTRATION

9.1 STUDY DOCUMENTATION

The investigator must maintain adequate and accurate records to enable the conduct of the study to be fully documented, including, but not limited to, the protocol, protocol amendments, Consent Forms, and documentation of IRB/EC and governmental approval. In addition, at the end of the study, the investigator will receive the patient data, including an audit trail containing a complete record of all changes to the data.

9.2 PROTOCOL DEVIATIONS

The investigator should document and explain any protocol deviations. The investigator should promptly report any deviations that might have an impact on patient safety and

data integrity to the Sponsor and to the IRB/EC in accordance with established IRB/EC policies and procedures.

